7.2.2 Clinical laboratory tests

The following clinical laboratory tests will be performed in the laboratory of each center. Clinical laboratory tests will comprise the following parameters:

Panel name	Laboratory parameters included
Hematology	leukocytes, erythrocytes, hemoglobin, hematocrit, thrombocytes (platelets); differential white blood cell count (neutrophils, lymphocytes, monocytes, basophils, eosinophils)
Chemistries - Enzymes - Substrates - Electrolytes	AST/SGOT, ALT/SGPT, gamma-GT, alkaline phosphatase, LDH total protein, total bilirubin, creatinine, urea, uric acid sodium, potassium, calcium
Urinalysis	glucose*, protein*, microalbumin**
Hormones	luteinizing hormone (LH), follicle stimulating hormone (FSH)
Pregnancy test	β-HCG (in serum; for women of childbearing potential only)

* In case there is no possibility for evaluation of the parameters provided above semiquantitative dipstick analysis will be accepted

** In cases where 24-hour urine is not available to determine microalbumin, the microalbumin/creatinine ratio or microalbumin-specific urine sticks may be used instead.

For each value outside the normal range, the investigator must classify the clinical significance/relevance of the abnormality following the criteria defined above, in Section 7.2.1.3.

7.2.3 Vital parameters, body weight, and performance status

Vital parameters to be recorded comprise systolic and diastolic blood pressure, and pulse.

Body weight shall be recorded in kg (rounded to closest integer). Note: the current body weight shall be used for the estimation of the body surface area ([Appendix 1](#)), as the basis for the total dose to be administered. (Note: If the body weight is +/- 10% of the body weight measured at day 1 of the preceding cycle, the body weight measured at day 1 of the preceding cycle may be used for calculating the dose to be prepared in the pharmacy).

Performance status will be recorded according to the ECOG/Zubrod scale (see [Appendix 2](#)).

The investigator should comment in the respective section of the CRF on a change compared to screening that is considered as clinically relevant. Such comment should - as far as possible - provide some explanation for the change. For obligations regarding documentation of abnormalities in vital signs as AE see [Section 7.2.1.3](#).

7.2.3.1 ECG

The ECG will be recorded as scheduled in the flow-chart by means of a 12-lead (I, II, III, aVR, aVL, aVF, V₁-V₆) ECG system over a duration of 10 sec while the subjects will rest in supine position. The chart speed will be set at 25 mm/sec. The ECG patterns will be analyzed qualitatively with particular emphasis on changes in the T-wave duration and

morphology. The following will be computed by the ECG machine: heart rate, time intervals such as PQ/PR, QRS and QT interval, the heart rate corrected QTc interval calculated according to Bazett's formula ($QTcB = QT/\sqrt{RR}$) or Fridericia's formula ($QTcF = QT/\sqrt[3]{RR}$), where QTc is the QT interval corrected for rate, and RR is the interval from the onset of one QRS complex to the onset of the next QRS complex, measured in seconds.

The investigator should comment on the CRF on any deviation from normal that is considered clinically significant/relevant. If a finding is considered as clinically significant as defined in above, in [Section 7.2.1.3](#), it must also be documented on the CRF Adverse Events.

For recording and evaluation of ECGs within the pharmacokinetic sub-study, refer to [Appendix 7](#) of the protocol.

7.2.3.2 Left ventricular ejection fraction (LVEF)

Cardiac function will be monitored by either echocardiography (ECHO) or radionuclide ventriculography (RNV) / multigated radionuclide angiography (MUGA). The technique used for assessment should be consistent throughout the trial for a given patient.

RNV/MUGA should be used where good quality ECHO images cannot be obtained from a patient, e.g., because of concomitant lung disease.

If test results indicate deterioration in cardiac function during the study, the benefit of continued therapy should be carefully evaluated against the risk of producing irreversible cardiac damage. Patients with LVEF < 30% are at significant risk of congestive heart failure. See [Section 5.3](#) for withdrawal criteria.

7.3 Other

7.3.1 Characterization of LHRH receptor expression in tumor tissue

It is planned to determine the expression of LHRH receptors in patients' tumor specimens ('receptor status') and to correlate the receptor status with clinical outcome data.

An assay for LHRH receptor expression is currently under development and may become available prior to the end of patient recruitment. Therefore, archival FFPE specimens (blocks) must be retained at the site. Similarly, FFPE blocks must be prepared from any fresh biopsy material obtained during screening. Study sites will be instructed about the timing and specific conditions of the specimens to be submitted.

7.3.2 Quality of life (QoL)

QoL will be measured by the EORTC QLQ-C30 questionnaire [2, 9], supplemented by the Endometrial Cancer Module (QLQ-EN24) which is designed for patients with all stages of endometrial cancer treated with pelvic surgery, chemotherapy, radiotherapy or concomitant radio/chemotherapy [12].

Specimens of both questionnaires are provided in [Appendix 6](#).

7.3.3 Pharmacokinetic investigations

Detailed instructions for the collection, processing, storage and shipment of samples for pharmacokinetic investigations will be provided in a separate manual.

7.3.3.1 Sparse PK sampling

Sparse PK sampling of AEZS-108-treated patients will be performed at all investigational sites where feasible. Sparse PK sampling is expected in one cycle, either Cycle 1 or alternatively in a subsequent cycle of ongoing patients. The windows for the sampling are defined as follows:

Sample #	Time Window
1	within 60 minutes before end of the 2-hour infusion
2	between 30 and 60 minutes after the end of infusion (EOI)
3	between 120 and 180 minutes after EOI
4*	between 4 and 6 hours after EOI

*) optional, depending on feasibility

7.3.3.2 PK sub-study

The pharmacokinetic sub-study will be conducted at selected investigational sites; it is planned to involve 40 patients, 20 patients from each study arm. Procedures are described in [APPENDIX 7](#) of the protocol.

8 STUDY PROCEDURES

A flow chart of the study procedures is displayed on page 13.

8.1 Patient's informed consent and registration prior to screening

A patient who has been identified as a potential candidate for the study will be informed about the study, based on the IRB/IEC approved written patient information.

Each patient who has given written informed consent will be registered into an interactive web-based response system (IWRS) before starting study-specific screening procedures.

The IWRS will issue a unique, 4-digit patient number that will be used to identify the patient on all study-related documents and specimens.

8.2 Screening procedures (within 4 weeks before start of treatment)

The following information will be obtained and screening tests will be performed within 28 calendar days before start of study treatment, i.e., Cycle 1 Day 1:

- **Medical history** and concomitant diseases (general and cancer-related history including prior treatment)

- **Clinical assessments** (physical examination, ECOG performance status and vital signs with height, weight, blood pressure, pulse)
 - **Clinical laboratory** (hematology, chemistries, urinalysis, hormones, pregnancy test (in serum) for women of childbearing potential)
- **Cardiac function:**
 - 12-lead electrocardiogram (ECG)
 - Left ventricular ejection fraction (LVEF): Echocardiogram or MUGA
Note: In absence of intercurrent chemotherapy or cardiac medical history, results dating back up to 8 weeks will be acceptable.
- **Tumor imaging** (CT or MRI): Appropriate radiographic procedures to document extent of disease
Note: For a given patient, the same imaging method must be used at screening and at follow-up assessments.
- **Quality of Life:** EORTC questionnaires
- **Tumor tissue specimens for LHRH receptor assay:** FFPE archival tumor specimen or – where available – FFPE fresh biopsies obtained during screening will be retained for later analysis.

Patients who are found to be ineligible will be registered in the IWRS as “Screen failure”. The reason for screen failure will be captured categorically. Apart from demographic patient characteristics, no other detailed screening data will be captured.

8.3 Randomized allocation of study treatment

Patients who meet the eligibility criteria will be randomly allocated by central randomization in a 1:1 ratio to receive either AEZS-108 (Arm A) or doxorubicin (Arm B).

Start of study treatment (Cycle 1 Day 1) should be scheduled for the nearest feasible date, to ensure that screening investigations, in particular laboratory investigations or measurements, have been performed within 28 days prior to treatment start.

8.4 Procedures during treatment

8.4.1 Procedures on Cycle 1 Day 1 (date of first study treatment)

After randomization, but prior to first administration of study treatment, each patient will have the following assessments and tests:

- **Interval history** and symptom-directed examination
Findings to be recorded as Medical History / Concomitant Disease/Condition
- **Clinical assessments** (including ECOG performance status, blood pressure, pulse, and weight for BSA and dose calculation)
- **Clinical laboratory** tests (hematology, chemistries, urinalysis)
- **Eligibility criteria review**
In the absence of new findings that would violate any of the eligibility criteria,

except for Day 1 clinical laboratory tests, the patient may receive the allocated study treatment.

- **Study treatment**
Administration of allocated study medication at the recommended starting dose.
- **Sparse PK sampling (AEZS-108 treated patients only)**
Blood collections within the following time windows:
sample #1: within 60 minutes before end of the 2-hour infusion
sample #2: between 30 and 60 minutes after the end of infusion (EOI)
sample #3: between 120 and 180 minutes after EOI;
sample #4 (optional): between 4 and 6 hours after EOI.

A patient, in whom sparse PK sampling was not possible in Cycle 1, may have the samples taken at any subsequent cycle. It is not planned to have repetitive sparse sampling of the same patient during multiple cycles.
- **PK substudy (instead of ‘sparse PK sampling’, at selected investigational sites only)**
Procedures related to the PK substudy are described in Appendix 7 of the protocol.

8.4.2 Weekly procedures during Cycle 1

Once weekly controls during Cycle 1 will include the following:

- **Clinical assessments** (including blood pressure and pulse)
- **Clinical laboratory tests** (hematology, chemistries, urinalysis)
- **Adverse event** recording.

Retreatment is planned in 3-weekly intervals, i.e. Day 1 of new cycle is corresponding to Day 22 of the previous cycle. In case of incomplete recovery from hematological toxicity or adverse events, re-treatment may be delayed for up to 2 weeks, i.e. with appropriate supplementary weekly controls on Day 29 and Day 35 (see [Section 6.1.3](#)).

8.4.3 Procedures on Day 1 of Cycle 2-9

It will be allowed to schedule tests up to 3 days before the planned Cycle Day 1, to ensure availability of safety-relevant results prior to dosing.

- **Interval history** and symptom-directed examination
Adverse changes to be recorded as Adverse Events
- **Clinical assessments** (including ECOG performance status, blood pressure, pulse, and weight for BSA and dose calculation). Note: If the body weight is +/- 10 % of the body weight measured at day 1 of the preceding cycle, the body weight measured at day 1 of the preceding cycle may be used for calculating the dose to be prepared in the pharmacy.
- **Clinical laboratory tests** (hematology, chemistries, urinalysis, hormones)

- **Cardiac function:**
 - 12-lead electrocardiogram (ECG)
- **Study treatment**

If dose-limiting toxicities have been observed in a previous cycle, the dose of the study treatment will be reduced in the next cycle (as well as in further cycles), as specified in [Section 6.1.3](#) or [6.2.3](#).
- **Sparse PK sampling (AEZS-108 treated patients only)**

A patient in whom sparse PK sampling was not possible in Cycle 1 may have the samples taken at any subsequent cycle. It is not planned to have repetitive sparse sampling of the same patient during multiple cycles.

Blood collections within the following time windows:

 - sample #1: within 60 minutes before end of the 2-hour infusion
 - sample #2: between 30 and 60 minutes after the end of infusion (EOI)
 - sample #3: between 120 and 180 minutes after EOI;
 - sample #4 (optional): between 4 and 6 hours after EOI.

8.4.4 Procedures during Cycle 2-9

Depending on hematological toxicities and any safety issues observed during Cycle 1, scheduling of hematological controls and/or other investigations is at the discretion of the investigators. For tests performed by a laboratory not affiliated with the study site (e.g. mid-cycle controls by the patient's home doctor) copies of the external laboratory reports will be provided to the sponsor and results reported in the CRF.

Adverse findings in such controls/investigations/diaries that the investigator considers as clinically important/significant will be recorded as Adverse Event.

8.4.5 Procedures at the end of Cycle 3 and 6

The following assessments will be performed at end of Cycle 3 and Cycle 6, i.e. together with the assessments required to assure continuation of study treatment with Cycle 4 and Cycle 7, respectively.

- **Cardiac function:**
 - Left ventricular ejection fraction (LVEF): echocardiogram or MUGA

Note: Recommended to be conducted also at end of Cycle 7 and 8 (i.e., before start of Cycle 8 and Cycle 9, respectively) for both arms. Results are to be captured on the eCRF if there is an abnormal finding.
- **Quality of Life:** questionnaires
- **Tumor imaging (CT or MRI):** evaluation of time-point response by comparison with target and non-target lesions defined at screening (baseline)

8.5 Procedures at end of study treatment

A patient who is going off study treatment (see [Section 5.3](#)) – will have the assessments/investigations specified below.

As an end-of-cycle assessment, it should be scheduled 3 to 5 weeks (Day 21 to 35) after the last dose. Additional visits/assessments may be indicated to follow-up unresolved adverse events.

- **Interval history** and symptom-directed examination
- **Clinical laboratory** tests (hematology, chemistries, urinalysis, hormones)
- **Cardiac function:**
 - 12-lead electrocardiogram (ECG)
 - Left ventricular ejection fraction (LVEF): Echocardiogram or MUGA
- **Quality of Life:** questionnaires
- **Tumor imaging (CT or MRI):** evaluation of time-point response by comparison with target and non-target lesions defined at screening (baseline)
- **Final evaluations:** best response, reason for discontinuation, investigator's overall judgment on tolerability of study treatment

8.6 Post-treatment follow-up

A patient developing signs of cardiac failure during post-treatment follow-up will have LVEF and ECG evaluated; a left ventricular dysfunction of CTCAE Grade 4 will be reported as an SAE.

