7.2.1.2 Procedures in case of adverse events

Throughout the study, the patient will be questioned and/or examined by the Investigator or his/her designee for evidence of adverse events. The questioning of patients with regard to the possible occurrence of adverse events should be as non-specific as possible.

However, given that it is the site's responsibility to follow up all AEs, specific questions related to previously reported AEs with regard to their resolution or continuation must be asked.

All adverse events occurring during a study have to be documented, regardless of any assumption of a causal relationship, on the respective AE CRF. All events that occurred during the screening period should be documented as medical history. The investigator should ensure, e.g. by telephone call to the trial subject, to record all events that occurred within 28 days after the last exposure to study drug.

Documentation of adverse events includes date of onset and offset, pattern, duration, severity, impact, actions taken, seriousness, and outcome. The investigator should also

evaluate the probability of a causal relationship of the adverse event to the study medication as likely, possible, unlikely, or unrelated. Information provided in the Investigator's Brochure may support this evaluation.

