7.2.1.4 Reporting of serious adverse event

The investigator must report serious adverse events (SAE) occurring or observed from the day of first administration of the investigational drug on and until 4 weeks after last administration of the investigational drug (development of impaired cardiac function (ex. \geq grade 4 left ventricular systolic dysfunction) within 1 year after last administration of study drug should also be reported as an SAE); see page 2 for contact persons and email/phone/fax numbers. As soon as possible, but in no case later than 24 hours after the SAE has been noted, the "Serious Adverse Event Report" form (*copies included in the Investigator's File*) should be sent by email, whether or not complete information is available within this period. In case of incomplete information, the investigator has to provide follow-up information as soon as possible, again using the SAE report form.

Regarding hospitalization, please refer to [Section 7.2.1.1](#), footnotes A and C for circumstances that will determine the consideration as SAE and need for reporting on an SAE form to AEZS drug safety.

All events that meet the definition of serious but, in the opinion of the treating investigator, are clearly expected from the patient's disease or related to disease progression (i.e., there exists no reasonable possibility that they were caused by the study drug) should be reported on the case report forms and do not require immediate reporting on an SAE form.

This will also apply to patient's death that is clearly attributed to the underlying malignant disease.

Reports will be evaluated by Aeterna Zentaris and authorities will be informed according to national or international regulations. The same information will also be made available to principal investigators of other currently ongoing trials with the same study medication.

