8.6.2 Follow-up for survival

For patients going off study, survival information will be collected at 3-month intervals, telephone contact is acceptable.

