APPENDIX 2: ECOG PERFORMANCE STATUS SCALE

Grade	Descriptions
0	Normal activity. Fully active, able to carry on all pre-disease performance without restriction.
1	Symptoms, but ambulatory. Restricted in physically strenuous activity, but ambulatory and able to carry out work of a light or sedentary nature (e.g., light housework, office work).
2	In bed <50 % of the time. Ambulatory and capable of all self-care, but unable to carry out any work activities. Up and about more than 50 % of waking hours.
3	In bed >50 % of the time. Capable of only limited self-care, confined to bed or chair more than 50 % of waking hours.
4	100 % bedridden. Completely disabled. Cannot carry on any self-care. Totally confined to bed or chair.
5	Dead.

**APPENDIX 3: GRADING OF LEFT VENTRICULAR FUNCTION
(CTCAE-V4.03)**

Adverse Event Category: Cardiac general

Adverse Event / Short Name: Left ventricular systolic dysfunction

Grade 1	Grade 2	Grade 3	Grade 4	Grade 5
-	-	Symptomatic due to drop in ejection fraction responsive to intervention	Refractory or poorly controlled heart failure due to drop in ejection fraction; intervention such as ventricular assist device, intravenous vasopressor support, or heart transplant indicated	Death

Adverse Event Category: Investigations

Adverse Event / Short Name: Ejection fraction (EF) decreased

Grade 1	Grade 2	Grade 3	Grade 4	Grade 5
-	Resting EF 50 – 40 %; 10 – 19 % drop from baseline	Resting EF 39 – 20 %; > 20 % drop from baseline	Resting EF < 20 %	Death

Source: CTCAE v4.03 publish date: June 14, 2010)

(see: http://evs.nci.nih.gov/ftp1/CTCAE/CTCAE_4.03_2010-06-14_QuickReference_5x7.pdf)

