1.4 Acute effects of doxorubicin on cardiac function

Early cardiotoxicity of doxorubicin consists mainly of sinus tachycardia and/or electrocardiogram (ECG) abnormalities such as non-specific ST-T wave changes. Tachyarrhythmias, including premature ventricular contractions and ventricular tachycardia, bradycardia, as well as atrioventricular and bundle-branch block have also been reported. These effects do not usually predict subsequent development of delayed

cardiotoxicity, are rarely of clinical importance, and are generally not considered an indication for the suspension of doxorubicin treatment.

Accordingly, a standard 12-lead ECG recording and 'rhythm strip' evaluation is considered sufficient for the monitoring of cardiac effects within this PK sub-study, which is limited to Cycle 1 dosing.

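### After the 28-day adverse event window, late cardiac events are captured passively and under reporting rules that disagree, so post-therapy LVEF percentages are not comparable incidences by arm

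*Protocol*

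**What the plan says.** **General windows.** Protocol 7.2.1.2 asks the investigator to "record all events that occurred within 28 days after the last exposure to study drug". Protocol 7.2.1.4 requires SAE reports "until 4 weeks after last administration of the investigational drug".

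**Late cardiac rule, in two forms.** Protocol 7.2.1.4 adds an exception. It opens with "development of impaired cardiac function (ex", gives Grade 4 or higher left ventricular systolic dysfunction as the example, and says that such an event "within 1 year after last administration of study drug should also be reported as an SAE". Protocol 8.6 and flow-chart footnote 9 (repeated in SAP Appendix A) say that signs of cardiac failure after treatment lead to LVEF and ECG, and that "a left ventricular dysfunction of CTCAE Grade 4 will be reported as an SAE". They give no time limit and no example wording.

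**Grades.** Protocol Appendix 3 defines Grade 3 left ventricular systolic dysfunction as "Symptomatic due to drop in ejection fraction responsive to intervention". Grade 4 is failure that is refractory or poorly controlled.

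**Contacts.** The last scheduled LVEF and ECG are at the end-of-treatment visit, 3 to 5 weeks after the last dose (Protocol 8.5). Visits until progression list ECOG status, blood pressure, pulse, imaging and quality of life (8.6.1). Under 8.6.2, "For patients going off study, survival information will be collected at 3-month intervals, telephone contact is acceptable".

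**Analysis.** SAP 9.5.1 tabulates LVEF falls and low values at post-therapy follow-up and cumulatively after the first dose. SAP 9.5.2 carries ECG categories to post-therapy follow-up. SAP 9.1 treats related events as treatment-emergent whatever their start date.

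**The concern.** Comparing safety is a stated secondary objective, and both arms deliver doxorubicin. The protocol's own background (Appendix 7, section 1.4) says of acute ECG changes: "These effects do not usually predict subsequent development of delayed" cardiotoxicity. Monitoring during treatment therefore cannot stand in for late follow-up.

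After treatment, two things go wrong. The reporting threshold depends on which section a site follows, and the difference falls on Grade 3, the treatable form of heart failure. Detection also depends on symptoms happening to reach the site, in a trial where the investigator knows the arm. If late cardiac rates are then set side by side, a difference or its absence could reflect who was looked at and which rule was applied, as well as the drugs. The direction cannot be predicted.

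**Working it through.** **1. The rules side by side**

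| Place | What is captured | Grade scope | Time limit |
|---|---|---|---|
| Protocol 7.2.1.2 | Any AE | Any | 28 days after last exposure |
| Protocol 7.2.1.4, general | SAE | Seriousness criteria | 4 weeks after last dose |
| Protocol 7.2.1.4, cardiac | Impaired cardiac function, as SAE | Grade 4 or higher as an example | 1 year |
| Protocol 8.6, footnote 9 | LVEF and ECG on signs of failure | Any for the tests; Grade 4 for the SAE | None |
| Protocol 7.2.1.3 | Clinically significant abnormal safety finding, as AE | Includes any that needed treatment; LVEF not named | None stated |
| Protocol 9.6.1 | Treatment-emergent AE | Any | Follow-up of last cycle; SAEs until resolved or stable |
| SAP 9.1 | Treatment-emergent AE | Any | End of study or 30 days after last dose, with no statement of which applies; related events without limit |

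**2. A test case.** Take a patient with Grade 3 symptomatic dysfunction 3 months after her last dose.
- 7.2.1.2: outside the window.
- 7.2.1.4, read broadly: reportable as an SAE. Read by its example: not reportable.
- 8.6 and footnote 9: LVEF and ECG are done, but the SAE clause does not apply.
- 7.2.1.3: an AE entry is arguable, because treatment was needed.

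Two sites acting in good faith can record her differently.

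**3. What would bring her to notice.** Visits before progression contain no cardiac question or test. The quality-of-life forms ask about breathlessness and leg swelling, but nothing links an answer to a cardiac work-up. Survival contacts ask for survival. Footnote 10 limits treatments recorded during survival follow-up to anticancer therapy, so a heart-failure drug would not reveal the event either.

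**4. How much follow-up lies beyond the 28-day window.** No figure in the plan measures late cardiac capture, so I size the period only.

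Inputs: median OS 9 months (doxorubicin) and 12 months (AEZS-108), 24 months of accrual and 12 of follow-up (Protocol 9.10); 250 per arm (Synopsis); 21-day cycles, at most nine for AEZS-108 (6.1.2). For doxorubicin, 550/60 = 9.2, so nine full cycles. Assumptions: exponential survival, no delays, every patient receiving the stated number of cycles c, and follow-up cut-off uniform between 12 and 36 months.

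Check of the survival model: the expected proportion dead is D = 1 − (e^(−12λ) − e^(−36λ))/(24λ), with λ = ln 2/median. This gives 0.819 and 0.730, so 250 × (0.819 + 0.730) ≈ 387 deaths, against about 384 in the plan.

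Window closes at w = [3(c − 1) + 4] weeks. Alive then: S = 2^(−w/median). Share of follow-up person-time beyond w: 1 − (1 − S)/D. For nine cycles, w = 28 weeks = 6.44 months; S = 2^(−6.44/9) = 0.609; share = 1 − 0.391/0.819 = 0.52.

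| Cycles | w (months) | Alive at w, dox / AEZS-108 | Of 250 per arm | Person-time beyond w |
|---|---|---|---|---|
| 3 | 2.30 | 84% / 88% | 209 / 219 | 80% / 83% |
| 6 | 4.37 | 71% / 78% | 179 / 194 | 65% / 69% |
| 9 | 6.44 | 61% / 69% | 152 / 172 | 52% / 57% |

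Some of that person-time falls after the 1-year limit in 7.2.1.4. The table describes time at risk, not missed events.

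**5. What the post-therapy LVEF figures represent.** After the end-of-treatment visit, LVEF is measured only in patients with signs of failure. SAP 9.5.1 states no denominator for its percentages. With tested patients as denominator, the group is selected by symptoms. With all treated patients, everyone untested is counted as having no decline. Neither gives an incidence that can be compared between arms.

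**The case against.** The strongest reply is that Grade 4 is an SAE threshold, not a recording threshold. Signs of cardiac failure trigger LVEF and ECG at any grade, with no stop at progression: the flow chart writes that limit for ECOG and blood pressure but not for these rows. The post-therapy AE row carries the same cardiac footnote, so AE recording is foreseen there. Protocol 7.2.1.3 points to an AE entry for findings that needed treatment, SAP 9.1 counts related events whatever their date, and SAP 9.5 tabulates the results. LVEF is also scheduled alike in both arms up to the end-of-treatment visit.

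This stands against a stronger reading. A reader might infer that the trial cannot see treatable late heart failure, or that only its refractory form is counted. The documents do not support that. What the reply leaves untouched is elicitation: these provisions handle an event once it is known, and none asks for it.

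A reader might also infer a detection bias favouring the arm with shorter PFS, because clinic visits end at progression. That is plausible, but the visits contain no cardiac item and the documents assume no PFS median for either arm. The nearest figure is a Phase II time to progression of about 7 months, in a study where 10 of 43 patients had prior chemotherapy. The effect cannot be sized. Nor does 28/365 (8%) measure cardiac capture, since the symptom trigger continues after day 28.

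Finally, SAP 9 treats formal safety comparisons as post-hoc, and patients may receive other anticancer therapy after study treatment, which complicates attribution. Both points are fair and limit the weight of the concern.

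**Conclusion.** The point holds in a limited form. The late cardiac rule differs between Protocol 7.2.1.4 and Protocol 8.6 with footnote 9, in both grade scope and time limit. Capture after the end-of-treatment visit is passive, and post-therapy LVEF summaries are symptom-selected in an open-label trial.

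Under the plan's OS medians and the assumptions above, 61–88% of patients are alive when the 28-day window closes, and at least half of follow-up person-time lies beyond it. The documents give no late heart-failure rate, so the number of incompletely captured events is unknown and could be small. The primary OS analysis is unaffected.

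**What to change.** 1. **Protocol 7.2.1.4, 8.6 and footnote 9.** Reconcile into one recording rule with one stated grade scope and one time limit; the 1-year window in 7.2.1.4 is available. State that symptomatic left ventricular dysfunction or diagnosed heart failure in that window is recorded as an AE whatever the progression status, and as an SAE where it meets the SAE criteria. This concerns recording only.
2. **Protocol 8.6.1 and 8.6.2.** Add one heart-failure question to the 3-monthly contacts already made during that year.
3. **SAP 9.1.** Say which end of the treatment-emergent window applies, and align it with Protocol 9.6.1. Tabulate these events by arm among treated patients, as cumulative incidence with death as a competing event, and note subsequent anticancer therapy.
4. **SAP 9.5.1.** Label post-therapy LVEF summaries as symptom-triggered and state their denominator. This can be done even if collection can no longer change.

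Cost: one CRF item, one table, some extra reporting, and verification of events first reported by telephone. Events after progression may partly reflect later therapy, so the table needs that caveat.
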